3.0 OBJECTIVES

3.1 Primary Objective

Determine the sensitivity and specificity of relative cerebral blood volume (rCBV) measured by steady state MRI with ferumoxytol in identifying true vs pseudoprogression in patients with newly diagnosed GBM receiving pembrolizumab with standard of care chemo-radiation.

3.2 Secondary Objectives:

1. Determine the safety and toxicity of pembrolizumab when used in combination with standard of care chemo radiation.
2. Determine the progression free survival (PFS), overall survival (OS), clinical response and duration of best response.

Rationale: Given the relatively small sample size, we aim to collect preliminary data on safety and toxicity as well as progression free survival, overall survival, best response and duration of best response survival. Data from this pilot study will be used to power a larger study.

3.3 Exploratory Objectives:

1. Compare the immune response as determined by the volume, pattern and intensity of delayed (24hr) ferumoxytol uptake between subjects who develop true vs pseudoprogression. This is optional and will be performed only in patients who have provided additional consent.
2. Investigate the serum immunological parameters (serum biomarker) and correlate clinical as well as radiological response with systemic immune response to pembrolizumab as measured by immunological panel.

3. Compare the changes in PDL-1 expression in the biopsy tissue before and after therapy at the time of progression and correlate PD-L1 expression with response rates and survival.
4. In subjects in metastatic arm with any measurable systemic lesions, investigate the feasibility of measuring vascular volume fraction (VVF), vessel size index (VSI) and vessel density index (VDI) as surrogate for response (true vs pseudoprogression, as determined by RECIST 1.1 and irRC [1, 2].

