10.0 STATISTICAL ANALYSIS PLAN

Given the exploratory nature of this study, the statistical analyses will be descriptive in nature. For the primary and secondary objectives, sensitivity, specificity, rate of adverse event and distribution of best responses will be analyzed using proportions and exact 95% confidence intervals. Progression free survival and overall survival will be assessed using the Kaplan-Meier product limit estimates. Outcomes in the exploratory objectives will be summarized using descriptive statistics as appropriate; and associations between immunological parameters, PDL-1 expression, clinical responses, radiological responses and other variables will be explored using two sample tests or correlation measures, as appropriate.

Power and sample size calculation for Arm 1

The accrual to arm 1 is stopped with 2 patients. These 2 patients will be described separately and no further analysis will be done.

Power and sample size calculation for Arm 2

For arm 2, we will enroll 43 GBM patients. Here we roughly estimate the precision of sensitivity and specificity in the primary objective based on these 43 patients.

In subjects with GBM, we anticipate to have only one lesion/subject. We assume that all subjects will eventually have disease progression and due to dropout and inoperable cases, a total of $n = 32$ subjects will undergo surgery to provide histopathological data on disease progression. Further, we assume that 40% of the $n = 43$ subjects will develop pseudo-progression and be observed based on follow-up scan.

For sensitivity, further assume that out of the $n = 32$ subjects who will undergo surgery, 26 subjects will have true progression based on pathology (gold standard). Then based on $n = 26$,

if we observe 22 subjects (lesions) for whom the true progression is correctly identified by Ferumoxytol MRI, then the sensitivity will be 85% with a 95% CI between 65% and 96% (Table XX).

Number of subjects (lesions) with true progression	Number of subjects (lesions) whose true progression was detected by Ferumoxytol MRI	Sensitivity	Exact 95% CI of Sensitivity
26	26	100%	87% to 100%
26	24	92%	75% to 99.1%
26	22	85%	65% to 96%
26	20	77%	56% to 91%
26	18	69%	48% to 86%
26	16	62%	41% to 80%

Table 12: Estimated sensitivity and 95% CI based on 26 subjects (lesions).

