For specificity, it will be calculated based on patients with pseudo-progression determined by either surgical results or follow-up scan. We assume that 40% of the subjects (n = 17) will develop pseudo-progression, then if we observe 15 subjects (lesions) for whom the pseudo-progression status is correctly identified by ferumoxytol MRI, the specificity will be 88% with a 95% CI between 64% and 99% (Table 13).

Number of lesions with pseudo-progression	Number of Lesions with pseudo-progression detected by Ferumoxytol MRI	Specificity	Exact 95% CI of Specificity
17	17	100%	80% to 100%
17	15	88%	64% to 99%
17	13	76%	50% to 93%
17	11	65%	38% to 86%

Table 13: Estimated specificity and 95% CI based on 17 patients.

Statistical Analysis

For arm 2, sensitivity, specificity, rate of adverse events (safety and tolerability) and the distribution of best responses will be analyzed using proportions and exact 95% confidence intervals. In the primary analysis of sensitivity and specificity, the cutoff for rCBV will be specified as 1.75 (<1.75 is pseudoprogression and ≥ 1.75 is progression). Analysis of sensitivity will be based on patients with surgical results, and specificity analysis will be based on patients with pseudo-progression determined based on surgical results or follow-up clinical scan, as detailed in the power and sample size calculation section. In secondary analysis, we will try other cutoff points for rCBV, and include all patients that will be confirmed with true progression through surgery or follow up imaging. Progression free survival and overall survival will be assessed using the Kaplan-Meier product limit estimates for all patients, taking censoring into account. For exploratory objectives, continuous variables will be summarized

using mean and standard deviation, or median and range based on the distribution of data. The categorical variables will be summarized using frequencies and proportions, with exact 95% CI as appropriate.

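### The unspecified secondary search over rCBV cut-offs needs an ROC analysis and an optimism correction; the primary analysis at 1.75 is unaffected

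*Combined protocol and SAP*

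**What the plan says.** Section 10.0 (Statistical Analysis) is clear about the primary analysis: "In the primary analysis of sensitivity and specificity, the cutoff for rCBV will be specified as 1.75". Sections 3.4 and 4.0 take that value from earlier studies, not from this trial.

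The secondary analysis is open: "In secondary analysis, we will try other cutoff points for rCBV". The same sentence widens the set to include true progression confirmed by follow-up imaging as well as by surgery. The SAP does not list the cut-offs, give their number or range, or say whether one will be chosen and by what rule. It mentions no ROC curve, AUC, resampling or validation set. The only estimator it gives for sensitivity and specificity is a proportion with an exact 95% CI.

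The sizing rests on "For arm 2, we will enroll 43 GBM patients", with 26 pathology-confirmed true progressions, and for specificity "We assume that 40% of the subjects (n = 17) will develop pseudo-progression".

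Section 3.2 adds, in the rationale for the safety, survival and response objectives, "Data from this pilot study will be used to power a larger study". Section 4.3.6 repeats this after listing the secondary endpoints.

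**The concern.** rCBV is continuous. When several cut-offs are tried on one small data set and the best is reported, part of its apparent advantage is chance. The raw proportions are then too high on average, and the exact CI treats the chosen cut-off as if it had been fixed beforehand.

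The SAP neither plans this selection nor rules it out. The protocol's background already compares thresholds: section 4.0 cites accuracy at a cut-off above 2.0, and survival prediction at four cut-offs. A reader of the results could therefore meet a preferred new cut-off with flattering accuracy figures and no sign of how much is due to selection. Those figures could also enter the planning of the next study.

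**Working it through.** **1. The plan's own figures.** Clopper-Pearson limits reproduce all ten rows of Tables 12 and 13 to rounding.
- Sensitivity 22/26 = 84.6%, CI 65.1% to 95.6%; half-width (95.6 − 65.1)/2 = 15.3 points.
- Specificity 15/17 = 88.2%, CI 63.6% to 98.5%; half-width (98.5 − 63.6)/2 = 17.5 points.
- 0.40 × 43 = 17.2, taken as 17.

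**2. Simulation set-up.** There were 20,000 trials per scenario, each with 26 true progressions and 17 pseudoprogressions.
- Assumption: log-rCBV is normal with equal SD in both groups.
- True sensitivity/specificity at 1.75 was set to values from Tables 12 and 13: 85%/88%, 77%/76% and 69%/65%.
- By AUC = Φ[(z_sens + z_spec)/√2], these correspond to AUCs of about 0.94, 0.85 and 0.73.
- In each trial the cut-off with the largest Youden index (sensitivity + specificity − 1) was chosen. Apparent accuracy was compared with true accuracy at that same cut-off.
- The two fixed grids also assume a log-rCBV SD of 0.4, which the documents do not give.

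**3. Mean overstatement (apparent minus true, in points).**

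| True sens/spec at 1.75 | Choice from all observed values | Choice from 5 cut-offs (1.25 to 2.25) | Choice from 3 cut-offs (1.5, 1.75, 2.0) |
|---|---|---|---|
| 85%/88% | +3.8 / +6.0 | +2.7 / +4.2 | +2.1 / +3.3 |
| 77%/76% | +5.0 / +7.5 | +3.2 / +5.0 | +2.5 / +3.7 |
| 69%/65% | +5.7 / +8.8 | +3.7 / +5.7 | +2.6 / +4.2 |

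In the top-left cell, apparent 89.1%/91.1% compares with true 85.3%/85.1%. The fixed 1.75 cut-off shows no bias in that scenario: 85.0%/88.1% on average against 85%/88%.

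Setting the AUC directly gives the same picture. At AUC 0.85, apparent 80%/83% compares with true 75%/75%. At AUC 0.70, 69%/72% compares with 63%/63%.

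**4. Exact-CI coverage at the selected cut-off.**
- Selecting from all observed values, coverage for sensitivity/specificity was 97.5%/97.8%, 95.8%/96.0% and 95.2%/95.0% in the three rows above.
- Placing the cut-offs at the observed values rather than midway between them gave 94.2%/97.0% at AUC 0.85 and 93.0%/95.9% at AUC 0.70.
- In those last two runs the misses lean one way. The sensitivity CI lay wholly above the truth in 5.9% of trials at AUC 0.85, against 0.8% for a fixed cut-off. At AUC 0.70 it was 7.0% against 2.2%.

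**5. Illustrative sizing effect.** Suppose a later study wants a CI half-width of 5 points (an assumption), with n = 1.96² p(1 − p)/0.05².
- True progressions: p = 0.891 gives 150; p = 0.853 gives 193.
- Pseudoprogressions: p = 0.911 gives 125; p = 0.851 gives 195.

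**The case against.** The SAP says it will try cut-offs. It does not say it will search for an optimum or adopt one. A table of sensitivity and specificity at several cut-offs, with none singled out, carries no selection bias and is in effect a coarse ROC curve. That stands, so the overstatement is conditional on selection.

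The main safeguard is already in place, because 1.75 is fixed in advance and always reportable. That also stands.

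The plan calls itself descriptive and tests no formal hypothesis, so an absent bootstrap correction is not an error in itself. This is fair, but a descriptive label does not remove bias from a number that is reported.

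Two stronger readings are tempting and should be resisted:
- A reader might infer that the larger study will be mis-sized. The power statement in sections 3.2 and 4.3.6 sits with safety, survival and response. Neither place ties sizing to rCBV accuracy or to a re-selected cut-off.
- A reader might infer that the exact CIs fail badly. Their built-in conservatism absorbs most of the selection effect, and what remains is the one-sidedness of the misses.

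**Conclusion.** The point holds as a gap in the secondary analysis only. If a best cut-off is picked from these data and reported raw, sensitivity is overstated by about 2 to 6 points and specificity by about 3 to 9 points on average. Both are well inside the planned CI half-widths of about 15 and 17 points. Coverage stays near 95%, with misses mainly on the favourable side.

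The direction follows from selection itself. The size rests on the equal-variance normal model, Youden selection, accuracy in the range of the SAP's tables, and the primary counts of 26 and 17. The secondary set adds imaging-confirmed progressions, so its counts will differ. Mis-sizing of a later study is possible, not planned: it would need the uncorrected values to be used, and the documents name no estimate for that purpose. This is a cheap improvement, not a flaw in the primary result.

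**What to change.** Keep 1.75 as the primary cut-off. In section 10.0, replace the open-ended trial of other cut-offs with:
- an ROC curve and AUC with 95% CI, in the secondary set that adds imaging-confirmed true progression. State how that confirmation is made, since section 8.1 defines confirmed true progression by histopathology only;
- a statement that any cut-off derived from these data is hypothesis-generating;
- for any such cut-off, bootstrap optimism-corrected sensitivity and specificity, re-selecting the cut-off in each resample;
- a statement that any later sizing uses the 1.75 results or the corrected values.

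The cost is SAP wording, a few lines of code and slightly less favourable secondary figures. No extra subjects, visits or scans are needed.

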5.2 Subject Inclusion Criteria

In order to be eligible for participation in this trial, the subject must:

1. Be willing and able to provide written informed consent/assent for the trial.
2. Be ≥ 18 years of age on day of signing informed consent.
3. Have a life expectancy of at least 6 months.
4. Have a histologically confirmed diagnosis of: newly diagnosed glioblastoma (WHO Grade IV)
5. Have ECOG performance status of 0 or 1 on stable or reducing dose of steroids for symptom management (not more than 8 mg of dexamethasone or equivalent per day) for 5 days prior to enrollment. Change in glucocorticoid dose for any purpose other than to modulate symptoms from an adverse event. *Note: The use of physiologic doses (e.g., prednisone 10 mg) of corticosteroids may be approved after consultation with Merck & Co. Use of prophylactic corticosteroids to avoid allergic reactions (e.g. IV contrast dye) is permitted.*
6. At least 14 days from any major surgeries including brain biopsy before the start of study drug pembrolizumab.
7. Demonstrate adequate organ function as defined in Table 3.
8. Female subject of childbearing potential should have a negative urine or serum pregnancy within 72 hours prior to receiving the first dose of study medication. If the urine test is positive or cannot be performed or confirmed as negative, a serum pregnancy test will be required.
9. Female subjects of childbearing potential should be willing to use 2 methods of birth control or be surgically sterile, or abstain from heterosexual activity for the course of the study through 120 days after the last dose of study medication. Subjects of childbearing potential are those who have not been surgically sterilized or have not been free from menses for > 1 year. Male subjects should agree to use an adequate method of contraception, including but not limited to, abstinence from heterosexual activity starting with the first dose of study therapy through 120 days after the last dose of study therapy.
10. Subject is eligible for and agrees to receive standard of care radiation and temozolamide after biopsy or maximum safe surgical resection.

Table 3 Adequate Organ Function Laboratory Values

System	Laboratory Value
--------	------------------

Hematological	
Absolute neutrophil count (ANC)	≥1,500 /mcL
Platelets	≥100,000 / mcL
Hemoglobin	≥9 g/dL or ≥5.6 mmol/L without transfusion or EPO dependency (within 7 days of assessment)
Renal	

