8.0 RESPONSE ASSESSMENT, IMAGE PROCESSING AND BIOMARKERS

8.1 Definitions for Response assessment:

The study will use the following criteria for the assessment of brain lesions.

Complete response (CR): Complete disappearance of all enhancing abnormalities on clinical enhanced MRI scan (in the absence of gadolinium, ferumoxytol enhancement will be used). Some subjects will have a small but persistent enhancing abnormality on MRI related to biopsy or focal hemorrhage. It is often difficult to ascertain whether this represents a residual nidus of tumor or scar tissue. Adjunctive radiologic studies such as SPECT or PET as clinically indicated may be helpful, but often the nature of these abnormalities may only be determined by following the subject with serial scans. If this type of abnormality does not change or slowly involutes over time off therapy and corticosteroids, it is reasonable to categorize it as a CR.

Partial Response (PR): At least 50% decrease in the contrast enhancing lesion seen on MRI as compared to baseline imaging. In the event of multiple lesions, the determination of partial response will be based on the sum of the bi-dimensional measurements (greatest diameter x greatest perpendicular) across lesions AND no new sites of disease

Stable disease (SD): less than a PR but is not progressive disease.

Progressive disease (PD):

- **Suspected Radiographic Progression:** progression will be defined by a 20% increase in volume of enhancement compared to the best response on clinical standard of care MRI. At any time point if progression is suspected on the clinical scan, additional steady state ferumoxytol MRI will be performed within 7 days of the clinical scan. Progression will then be confirmed with a follow up scan in 4 weeks \pm 5 days with a clinical standard of care MRI scan and additional ferumoxytol scan.
- **Persistent Radiographic Progression:** sustained and evident progression greater than increase in volume of enhancement compared to best response on a follow up scan at least 4 weeks after the scan where progression was suspected as per RANO BM form arm 1 or RANO criteria for subjects in arm 2. In cases with persistent radiographic progression the date of initial scan when progression was suspected will be considered to be the date of progression.
- Appearance of any new lesion or site of disease in the brain during or at the end of therapy.

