- **Confirmation of true progression:** For the purpose of this study, Histopathologic evidence of viable tumor cells in patients with persistent radiographic progression will be define to have confirmed true progression. True progression is confirmed by histopathology, Pembrolizumab will be stopped and patient swill be taken off-study.. Patients who refuse biopsy or biopsy is not deemed clinically necessary will be taken off study at persistent radiographic progression. However, they will be continued to be monitored with clinical MRI scan and until death.
- **Pseudoprogression (PsP):** for the purpose of this pilot study, PsP may be confirmed by imaging or by pathology.
 - PsP Imaging: stable or decrease in volume of enhancement at 4 weeks (\pm 5 days) after suspected radiographic progression.
 - PsP pathology: No viable tumor tissue is seen by histopathology evaluation on tissue obtained after confirmed radiographic progression by imaging.
- **Clinical progression:** Subjects may be removed from study if they experience symptomatic deterioration without radiographic evidence of disease progression.

Not evaluable (NE): Only relevant if any of the target lesions had additional interventions for clinical managements, patient is unable to get follow up scans or images are of poor quality.

Duration of Best Response: The duration of best response is measured from the time measurement criteria are met for SD, CR or PR (whichever is first recorded) until the first date that recurrent or PD is objectively documented (taking as reference for PD the smallest measurements recorded since the treatment started).

Progression free survival and overall survival will be calculated from the date of diagnosis to the date of confirmed progression or death, respectively. The date of diagnosis was used because the time between the date of diagnosis and the start of treatment or date of enrollment may vary due to subject variables or logistical issues based on radiation planning.

Systemic Lesions (only for Arm 1):

Measurements based on RECIST version 1.1 will be used to make a diagnosis of suspected systemic progression; it will be confirmed using irRC at follow-up.

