Exploratory objectives 1 to 3 will be analyzed using patients from arm 2. Immune responses will be determined by the volume, pattern and intensity of delayed (24hr) ferumoxytol uptake and compared between patients who develop true vs. pseudoprogression and provided data using Wilcoxon Rank Sum test (volume and intensity) or Fisher's exact test (pattern). Systemic immune responses will be measured by immunological parameters (CD3, CD4, CD8, CD19, CD25, CD27, CD45, CD56, CD45R0, CD45RA, titers of IgD, $T\gamma\delta$ and $T\alpha\beta$) and correlated with clinical responses (complete response, disease progression, pseudoprogression etc.) using Wilcoxon Rank Sum test, and with radiological response (size of tumor) using Pearson's correlation coefficient or Spearman's correlation coefficient.

For exploratory objective 3, among the 43 patients, 8 to 10 patients are expected to have data on PD-1 receptor expression (Yes vs. No, where Yes is defined as $\geq 1\%$ PDL-1 expression and No as $< 1\%$ based on FDA recommendations <https://www.keytruda.com/static/pdf/keytruda-pd-l1-expression-testing-guide.pdf>) and immune cells (T cells, CD4+, CD8+, macrophages, M1, M2 etc) before initiation of Pembrolizumab and at the time of progression. If data allow, we will compare the PD-1 receptor expression and immune cells data before initiation of Pembrolizumab and at the time of progression using exact McNemar's test or Wilcoxon signed test to accommodate the paired nature of the data, and use univariate logistic or Cox regression models to correlate PD-L1 expression with response rates and survival. Lastly, in metastatic patients with measurable systemic lesions, vascular volume fraction (VVF), vessel size index (VSI) and vessel density index (VDI) will be measured and compared between patients with true vs. pseudoprogression, if data allow.

In summary, all these proposed analyses will be conducted on the exploratory basis. A two-sample t-test may be used if the data show adequate normality. We will only provide descriptive statistics if the comparison mentioned above won't yield clinical meaningful results. The purpose of these exploratory analyses is to see whether some preliminary signals in the data could be detected.

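### Exploratory objective 2 takes radiological response as tumour size, so that correlation describes tumour burden and dilutes any link with response

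*Combined protocol and SAP*

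**What the plan says.** Exploratory objective 2 (Section 3.3) is to "correlate clinical as well as radiological response with systemic immune response to pembrolizumab as measured by immunological panel". Section 10.0 does this in two ways. The markers are compared across clinical response categories by Wilcoxon rank sum test. They are also correlated "and with radiological response (size of tumor) using" Pearson's or Spearman's coefficient. The second analysis has no change score, reference scan, time point or baseline adjustment, and no other section supplies one.

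Section 8.1 mostly judges radiological outcome by change, against differing reference scans:
- Partial response: "At least 50% decrease in the contrast enhancing lesion seen on MRI as compared to baseline imaging".
- Suspected progression: "progression will be defined by a 20% increase in volume of enhancement compared to the best response on clinical standard of care MRI".
- Imaging pseudoprogression: "stable or decrease in volume of enhancement at 4 weeks" after the scan that raised the suspicion.
- Complete response is the exception. It is the disappearance of enhancement, an absolute state.

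Subjects start radiation and temozolomide "after biopsy or maximum safe surgical resection" (Section 5.2). Blood sampling is optional and is tied to the ferumoxytol scans at baseline, 4 weeks after radiation, suspected progression and 4 weeks later (Section 8.3.1).

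**The concern.** Size at a follow-up scan is baseline size plus whatever has happened since. Baseline enhancing volume will vary for surgical reasons, because some subjects have had only a biopsy and others a resection. Take two invented lesions: one shrinks from 40 to 20 units, a partial response, and one grows from 4 to 12. Raw size ranks the responder as the worse case.

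Two things follow. A marker related to baseline size, and not to response, can appear as a correlate of response. A marker that does follow response is blurred by baseline spread it has nothing to do with. The stated purpose of these analyses is to look for preliminary signals, so a variable that adds burden signals and weakens response signals works against it.

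**Working it through.** **The plan's own figures.** The SAP gives no planning figure for this correlation. Its only planning figures are the exact intervals in Tables 12 and 13. All ten reproduce to rounding (for example 22/26 gives 65.1% to 95.6%), but they do not bear on this point.

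**Inputs from the documents.** At most n=43 (Section 10.0), and fewer if subjects decline the optional blood draws.

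**Inputs assumed, because the documents give none.** SD of log baseline size (s_B) and of log change (s_C), each 0.5 to 0.8; the marker correlations; a two-sided 0.05 threshold; baseline and change independent unless stated.

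**Model.** Log follow-up size = B + C, with B baseline and C change. Under independence:
- marker linked only to baseline (correlation r_B): correlation with size = r_B × s_B / √(s_B² + s_C²)
- marker linked only to change (correlation r_C): correlation with size = r_C × s_C / √(s_B² + s_C²)

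**Numbers in.** In both mixed settings √(0.64 + 0.25) = 0.943.
- s_B 0.8, s_C 0.5: r_B = -0.4 carries over as -0.4 × 0.8/0.943 = -0.34; r_C = -0.5 shrinks to -0.5 × 0.5/0.943 = -0.27.
- s_B 0.5, s_C 0.8: r_B = -0.4 carries over as -0.21; r_C = -0.5 shrinks to -0.42.

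**Simulated Spearman results, n=43.** A dash means not tabulated.

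| s_B, s_C | p<0.05 on size, marker tied to baseline only (r -0.2 to -0.4) | Power on size, r_C = -0.5 | Power on change |
|---|---|---|---|
| 0.8, 0.5 | 18%, 35%, 56% | 36% | 91% |
| 0.8, 0.8 | – | 60% | about 91% |
| 0.5, 0.8 | 10% to 25% | 78% | 91% |

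With change as the variable, the baseline-only marker reaches p<0.05 about 5% of the time. At n=25 with SDs 0.8 and 0.5, the size-based figures are about 12% to 35%, and power is about 23% on size against 69% on change. A setting with more baseline spread and less change (1.0 and 0.3) lowers power on size to 14% at n=43.

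**Relaxing independence.** Suppose change correlates -0.5 with baseline, so that larger lesions shrink more. A marker tied only to baseline then also correlates with simple change, which gives p<0.05 in 10% to 23% of trials; partial Spearman given baseline stays near 5%. The same dependence weakens the false link with raw size. Size then correlates with baseline at (s_B - 0.5 s_C)/√(s_B² + s_C² - s_B s_C). For SDs 0.5 and 0.8 this is 0.1/0.7 = 0.14, so r_B = -0.4 carries over as only -0.06. For SDs 0.8 and 0.5 it is 0.55/0.7 = 0.79, so it carries over as -0.31.

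**Cost of the adjusted analysis.** When baseline is unrelated to the marker, partial Spearman has power of about 86% to 89%, against 91% for simple change.

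**The case against.** A reader might infer that a wrong null hypothesis is being tested at an inflated error rate. The documents do not support that. Section 3.4 says there is no formal hypothesis, Section 10.0 calls the analyses descriptive, and no alpha is set. The 0.05 used here is only a yardstick. The coefficient itself still describes burden, so the point survives without a test.

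A reader might also infer that the whole biomarker objective would report burden as response. It would not. The Wilcoxon comparison in the same sentence of Section 10.0 uses response categories such as progression and pseudoprogression. What is affected is the separate radiological analysis, the only one of the two with a continuous measure.

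The parenthesis may be shorthand for change in size. That is possible, but nothing in the documents says so; if it is meant, the wording should say it.

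Nor does Section 8.1 define response solely against baseline: best response and the suspected-progression scan are also references. Change from baseline alone would therefore not match progression or pseudoprogression.

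Finally, steroids are one plausible route from lesion size to markers, though that larger lesions receive more steroid is an inference. Sections 4.0 and 4.2 already plan a separate analysis by bevacizumab and steroid dose. Section 4.0 also says steroids can alter imaging, so correlating marker change with size change would not remove this confounding.

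**Conclusion.** The point holds as a limited one. The variable named for radiological response measures burden, while the objective and most of Section 8.1 concern change. With independent baseline and change and the assumed SDs, a baseline-only marker would look associated in about 10% to 56% of trials at n=43. Power for a true correlation of -0.5 with change would be 36% to 78%, against about 91%. These sizes rest on SDs and correlations the documents do not give. The loss of power shrinks to 13 points (91 - 78) when change varies more than baseline, and the false link can almost vanish if large lesions also shrink most. The mismatch between variable and objective does not depend on those values. It is confined to one exploratory correlation, and it is worth correcting because the correction is nearly free.

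**What to change.** In Section 10.0, replace tumour size with a partial Spearman correlation of the marker with enhancing volume at the scan paired with the blood draw, given enhancing volume at the baseline scan. This copes with nil baseline enhancement and with change that depends on baseline. Change in volume from baseline can be a supporting measure. For draws at or after suspected progression, use the Section 8.1 reference scan in place of baseline: best response or the suspected-progression scan, as the definition requires. The baseline draw has no earlier scan, so state which later scan it is set against. If raw size is kept, report it as tumour burden. Keep the planned analysis by steroid dose, since this change does not replace it.

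The cost is SAP wording. Baseline scans are already scheduled and no new procedure is needed. Power is slightly lower than with simple change when baseline is unrelated to the marker, and subjects without a paired scan drop out.
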